7.3 III

Immediately after completing Part II, participants will receive a clinical assessment from a mental health professional (MHP). A web-conferencing tool link to their appointment will be provided in the confirmation email. Participants will be reminded that this is only a clinical assessment and will not involve treatment of any kind.

MHPs will fill out the Hamilton Depression Rating Scale (HAM-D) and Hamilton Anxiety Scale (HAM-A), keep a copy of the spreadsheet for their records and for subsequent data monitoring activities. Along with the spreadsheet, MHPs will send the concomitant medication log and clinical notes to the research coordinators. Some medications affect voice biomarkers and we want to be able to separate the effect of depression and anxiety vs medication from the voice biomarkers. The information is stored on a password protected location only accessible to the PI and the research coordinators. When the study is over, the Personal Health Information (the email addresses) will be deleted and coding will be used to match the records going forward.

Completion of this part will take about 30-minutes. The participant does not get a copy of their assessment and will not be able to see their assessment results.

Once participants have been evaluated by the MHP using the HAM-D and HAM-A the Research Coordinator will email the \$50 Amazon Gift card, PayPal or Visa cards.

Kintsugi staff and any data analysts will be blinded to the HAM-D and HAM-A scores.

The MHPs are either licensed mental health professionals or PhD students who have relevant experience assessing mental health patients as part of their course work. MHPs are remunerated at their market rate for conducting the clinical assessment. The MHPs do not provide any treatment to the participants. The MHPs provide a list of additional resources for the participant if they experience distress or discomfort (see page 2 of Participant Communication for Part II of Study Procedure attachment). MHPs are instructed not to establish any clinical relationship with the participant.

The MHPs are instructed to set all of their appointments with participants to private so that no one else can see these appointments. The MHPs have access to email addresses of the participants they assess because it's necessary to set up the video appointments. .

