4. STUDY DESIGN

This is a prospective, fully remote observational e-clinical study to improve the sensitivity and specificity of KiVA™ predictions against clinician-rendered HAM-D and HAM-A scores.

The duration of the study enrollment is anticipated to continue until ~1,000 participants are enrolled. We will extend the enrollment period until the necessary number of participants is enrolled.

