9. STATISTICAL CONSIDERATIONS

9.1 Study Outcome Measures

9.1.1 Primary Outcomes

- Hamilton Depression Rating Scale.
 - Participants will be interviewed by MHPs using the clinically validated HAM-D tool.
- Hamilton Anxiety Rating Scale.
 - Participants will be interviewed by MHPs using the clinically validated HAM-A tool.

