10.2 Participant Confidentiality

Participant confidentiality and privacy is strictly held in trust by the PI and staff. The study protocol, documentation, data, and all other information generated will be held in strict

confidence. No information concerning the study, or the data will be released to any unauthorized third party without prior written approval of the sponsor.

Authorized representatives of the Sponsor or representatives of the IRB may inspect all documents and records required to be maintained for the participants in this study. The Sponsor will retain the data gathered from this study indefinitely.

Participant confidentiality will be maintained by deleting the participants' Personal Identifiable Information (Email, Phone number, First and Last Name) once the study concludes.

Audio recordings will be stored on a password-protected Google Cloud Platform bucket indefinitely. Researchers will also be using Named Entity Recognition (NER) and number detection scripts to strip out any person names, organizations, locations, medical codes, quantities, medical record numbers, monetary values, and percentages after the study concludes. NER will be implemented using the NLTK library of Python.

The following documents will be retained after the study for a period of at least six years on a password-protected Google Cloud Platform bucket:

- Study protocol
- Informed Consent forms
- Participant recruitment ads
- PI and Research Coordinator's CVs
- PI and Research Coordinator's training certificates
- Amendments to the protocol
- Documentation of approval of amendments by IRB
- De-identified participant enrollment log
- Final report to IRB

The above listed electronic data will be deleted after 6 years. Data gathered from the study (audio recordings, HAM-D/HAM-A scores) will be stored indefinitely.

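### Section 7.3 blinds sponsor staff and all data analysts to HAM-D and HAM-A without scope or end, although section 4 aims at accuracy against those scores

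*Protocol*

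**What the plan says.** Under Part III (section 7.3), mental health professionals (MHPs) rate each participant on HAM-D and HAM-A and keep a copy of the score sheet. The section then says who receives it: "Along with the spreadsheet, MHPs will send the concomitant medication log and clinical notes to the research coordinators". On storage it adds: "The information is stored on a password protected location only accessible to the PI and the research coordinators". Later in the same section comes the blinding rule: "Kintsugi staff and any data analysts will be blinded to the HAM-D and HAM-A scores".

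Section 4 describes a study meant to improve the sensitivity and specificity of the software's "predictions against clinician-rendered HAM-D and HAM-A scores". Section 9.1.1 names HAM-D and HAM-A as the two primary outcomes; for the first it says "Participants will be interviewed by MHPs using the clinically validated HAM-D tool". Section 9.2 adds only that the collected data will be pooled to train a machine learning model.

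**The concern.** Sensitivity and specificity are computed by setting each prediction beside its reference score. The reference here is HAM-D and HAM-A, and the protocol withholds both from every data analyst without limit. Followed to the letter, the rule stops the comparison named in section 4.

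Two practical consequences follow. An analysis plan that released the scores to analysts would contradict the protocol. If the rule were instead set aside informally, no document would fix who received which scores and when. A reader of the results could then not tell whether the model builders had already seen the scores used to judge the model.

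**Working it through.** No arithmetic applies, because the protocol gives no figure on this point. The check sets the sections side by side.

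**1. What the aim needs.** Section 4 needs at least one person who may see a participant's HAM-D or HAM-A score and who is assigned to link it to that participant's audio or prediction.

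**2. Who may see the scores, and who analyses.**

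| Role | Access to scores | Analysis task stated |
|---|---|---|
| MHPs | Yes: they produce the scores and keep a copy (7.3) | None |
| Research coordinators | Yes: they receive the score sheet (7.3) | None |
| PI | Yes: storage access (7.3) | None |
| Sponsor staff | Blinded (7.3) | None named |
| Data analysts | Blinded, all of them (7.3) | Implied by the title |

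No row has both access and an analysis task.

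**3. Could a score-holder do the linking?** A coordinator could run a prepared program on predictions handed over by blinded analysts. No section assigns that task. The rule covers analysts of every kind, so a coordinator who took it on would arguably fall under the rule as well.

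**4. Does it matter whether coordinators are sponsor staff?** The text reviewed does not state their affiliation, and pages that might show it were not available. Both cases were tried:
- If they are sponsor staff, section 7.3 contradicts itself, because it sends them the scores to which it blinds them.
- If they are not, they hold the scores without an analysis task, and the conflict with section 4 remains.

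The conclusion is the same either way.

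**5. Is there a limit elsewhere?** Sections 2.3.1, 9.2, 10.2 and 11 were read for an exempt analyst, an unblinding step or an end of the blind. They deal with storage, access, retention and model training. None limits the rule.

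**The case against.** The strongest reply is that the blind was never meant to last. The sentence stands among the visit procedures, not in the analysis section. Section 7.3 says that after the study "coding will be used to match the records going forward", and section 10.2 says "Data gathered from the study (audio recordings, HAM-D/HAM-A scores) will be stored indefinitely". Neither makes much sense if the scores are never to be used. Section 3 frames the objective as collecting data, which fits a blind during collection with model work afterwards. Keeping model builders away from reference scores is also good practice, and the date of unblinding is often left to the SAP.

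Most of this stands: a time-limited blind is the likely intent. It does not remove the conflict, because an unqualified protocol rule is not narrowed by inference. Several intents also fit the text (a blind during collection, until predictions are fixed, or only for participants used in evaluation), and each gives model builders different access.

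A reader might infer more than the protocol supports:
- **That the rule also contradicts section 9.1.1 and the medication aim.** Section 9.1.1 lists outcomes and who administers them; blinding staff to a primary outcome during a study is ordinary. The remark that "we want to be able to separate the effect of depression and anxiety vs medication from the voice biomarkers" explains why a medication log is collected and schedules no analysis.
- **That model training under section 9.2 is impossible.** PHQ-9 and GAD-7 are collected in Parts I and II and are not blinded, so training on them remains open.
- **That the access statements disagree.** Section 11 refers to authorized personnel for the audio. These can be the PI and coordinators named in section 2.3.1.

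**Conclusion.** The concern holds in a narrow form. One sentence in section 7.3, as worded, defeats the accuracy aim in section 4. It is a contradiction within the protocol, not merely a detail left to the SAP.

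Its reach is both primary outcomes for all participants assessed in Part III. Their number is not stated; they come from those with PHQ-9 greater than 20 among about 1,000 enrolled. No effect on the accuracy estimates can be calculated. It would be tempting to conclude that accuracy will be inflated because model builders will see the evaluation scores, but nothing in the protocol says or implies that this will happen.

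The verdict assumes that no unseen page limits the blind. It does not depend on whether the coordinators are sponsor staff. The correction should be made, because it is cheap and concerns the central comparison.

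**What to change.** Keep the blind, and give it a scope and an end. The sentence in section 7.3 could be replaced by:

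> The PI and research coordinators hold the HAM-D and HAM-A scores under participant codes. Those who build the model or generate predictions are blinded to the scores of any participant used to evaluate the model until the predictions and threshold for that participant are fixed and dated; coded scores are then released for linkage. Coded scores of participants used for training may be released to the analysts once data collection is complete.

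Section 7.3 now mentions coding only for when the study is over. Codes must therefore be assigned earlier if any scores are released before then.

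Whether evaluation uses a held-out set or cross-validation split by participant can be left to the SAP; the protocol need not prescribe either. No change to audio access is asked for. Section 10.2 removes names and numbers from recordings only after the study concludes, so wider access before then would raise a separate confidentiality question.

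The cost is a protocol amendment, which section 10.1 requires the IRB to approve before it takes effect, and a later release of scores to model builders, who cannot use training scores until collection ends.

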8. PARTICIPANT WITHDRAWAL

Participants can withdraw from the study at any time. If a participant decided to withdraw, a participant is encouraged to:

1. Call or email the Research Coordinator.
2. Let the research coordinator know about their intention to withdraw.

If a participant doesn't follow the steps to complete the study 2 weeks after the enrollment, they will be considered as withdrawn.

9. STATISTICAL CONSIDERATIONS

9.1 Study Outcome Measures

9.1.1 Primary Outcomes

- Hamilton Depression Rating Scale.
 - Participants will be interviewed by MHPs using the clinically validated HAM-D tool.
- Hamilton Anxiety Rating Scale.
 - Participants will be interviewed by MHPs using the clinically validated HAM-A tool.

9.2 Data Analysis Plan

The data collected during this study will be aggregated and for training a machine learning model.

10. ETHICS/PROTECTION OF HUMAN PARTICIPANTS

The investigator will ensure that this study is conducted in full conformity with the principles set forth in The Belmont Report: Ethical Principles and Guidelines for the Protection of Human Subjects of Research, as drafted by the US National Commission for the Protection of Human Subjects of Biomedical and Behavioral Research (April 18, 1979) and codified in 45 CFR Part 46 and/or the ICH E6.

10.1 Institutional Review Board

The protocol, informed consent form, recruitment materials, and all participant materials will be submitted to the IRB for review and approval. Approval of both the protocol and the consent form will be obtained before any participant is enrolled. Any amendment to the protocol will be reviewed and approved by the IRB before the changes are implemented in the study.

10.2 Participant Confidentiality

Participant confidentiality and privacy is strictly held in trust by the PI and staff. The study protocol, documentation, data, and all other information generated will be held in strict

confidence. No information concerning the study, or the data will be released to any unauthorized third party without prior written approval of the sponsor.

Authorized representatives of the Sponsor or representatives of the IRB may inspect all documents and records required to be maintained for the participants in this study. The Sponsor will retain the data gathered from this study indefinitely.

Participant confidentiality will be maintained by deleting the participants' Personal Identifiable Information (Email, Phone number, First and Last Name) once the study concludes.

Audio recordings will be stored on a password-protected Google Cloud Platform bucket indefinitely. Researchers will also be using Named Entity Recognition (NER) and number detection scripts to strip out any person names, organizations, locations, medical codes, quantities, medical record numbers, monetary values, and percentages after the study concludes. NER will be implemented using the NLTK library of Python.

The following documents will be retained after the study for a period of at least six years on a password-protected Google Cloud Platform bucket:

- Study protocol
- Informed Consent forms
- Participant recruitment ads
- PI and Research Coordinator's CVs
- PI and Research Coordinator's training certificates
- Amendments to the protocol
- Documentation of approval of amendments by IRB
- De-identified participant enrollment log
- Final report to IRB

The above listed electronic data will be deleted after 6 years. Data gathered from the study (audio recordings, HAM-D/HAM-A scores) will be stored indefinitely.

11. DATA HANDLING AND RECORD KEEPING

Research records will be kept in compliance with ICH E6, Section 4.9 and regulatory requirements for the protection of confidentiality of participants. The Research Study staff will permit authorized representatives of regulatory agencies to examine (and when required by applicable law, to copy) research records for the purposes of quality assurance reviews, audits, and evaluation of the study safety, progress and data validity.

Audio recordings will be saved on a password-protected Google Cloud Platform bucket that is only accessible to authorized personnel.

The audio recordings and HAM-D/HAM-A score data will be maintained for at least three years following the completion of the study. Participant confidentiality will be maintained by deleting the participants' Personal Identifiable Information (Email, Phone number, First and Last Name) and using codes once the study concludes.

12. PUBLICATION POLICY

We anticipate submitting to a peer-reviewed journal, such as Nature's NPJ or Karger Digital Biomarkers.

